With the COVID-19 pandemic extra measures were taken to protect HF patients who are considered as clinically vulnerable (shielding). This impacted on patients access to treatment and health care services, community networks and support from family and friends. It is anticipated during the pandemic this has had a deleterious impact on individuals' mental health with increased social isolation, anxiety about care and treatment, and risk of poor outcome if contract COVID-19. This study will explore the impact of COVID-19 on the psychological wellbeing of community-based HF patients.

Research Question

How is depression and anxiety being assessed, managed and treated in community-based HF patients; and what is their views on the use of web-based intervention?

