Even though qualitative telephone interviews are used less frequently than the traditional face-to-face interviews (Opdenakker, 2006; Sweet, 2002), it can be a useful data collection method (Carr & Worth, 2001, p. 521). The participants of qualitative telephone interviews were found to feel more comfortable being interviewed over the telephone and talking more freely than face to face interviews (Novick, 2008). The qualitative data obtained from telephone interviews were reported to be rich, comprehensive and of high quality (Chapple, 1999; Kavanaugh & Ayres, 1998; Sturges & Hanrahan, 2004; Sweet, 2002). In comparison to face-to-face interviews, the qualitative telephone interviews were less costly (Chapple, 1999), can increase access to different geographically located participants (Sturges & Hanrahan, 2004; Sweet, 2002; Tausig & Freeman, 1988) and is safer for the interviewer (Carr & Worth, 2001; Sturges & Hanrahan, 2004). Qualitative telephone interview also allows more anonymity (Sweet, 2002; Tausig & Freeman, 1988), privacy (Sturges & Hanrahan, 2004), and decrease in social pressure (McCoyd & Kerson, 2006).

Qualitative methodology was deemed the best method to meet the study aims and to understand how community HF nurses are assessing, managing and treating depression and anxiety in community-based HF patients; and what they think of using a web-based Intervention (i.e. COMPASS). Qualitative methods are a useful method to explore the depth of participants' views and opinions related to an issue of interest, and to capture participants' interpretations regarding a concept. Online focus group is useful for the researcher to grasp how those who

take part perceive the process and feel comfortable including experiences and emotions around a particular topic (Barbour, 2005). Barbour (2005) highlights how focus group enables the researcher to observe record and analyse the group's interactions to include this in the presentation of findings.

Subject inclusion criteria

Inclusion criteria for Community-based HF patients:

- 1) Community-based HF patients with clinically established HF diagnosis (confirmed HF diagnosis) in Lambeth and Southwark Boroughs who have mild to moderate symptoms of depression with/without anxiety confirmed by PHQ-9 (5-14) and GAD-7;
- 2) Patients with NYHA class I-III;
- 3) Capacity to provide informed consent; and
- 4) Proficiency in English language so can fully respond to verbal and written material.

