The date of the online focus group will be decided according to community HF nurses' preferences. A time will be agreed with their manager when all of the community HF nurses can meet as a group. The PIS and consent form will be sent to all community HF nurses by email. The consent form will be signed ahead of time and gathered online. Similarly, baseline demographic data will be sent and collected online. The community HF nurses will be involved in the online focus group that will be conducted using Microsoft teams. A link to the online focus group will be sent by the researcher to all community HF nurses with the agreed date and time. The online focus group will have a skilled moderator who is the researcher's supervisor (co-investigator). The moderator will moderate the session and will deal with any arising technical issues.

The discussion with community HF nurses will include their perspectives about depression and anxiety assessment and management process and what they think of web-based intervention. Then, the community HF nurses will have a short break. Immediately after the break, a COMPASS team member will join the online focus group and will demonstrate the COMPASS web-based intervention to the community HF nurses. Community HF nurses will be allowed to ask questions regarding COMPASS before the COMPASS team member leaves the online focus group. Once demonstration is complete and the COMPASS personnel has left the online focus group, the researcher will take over and will assess community HF nurses' perspectives regarding COMPASS. The participants will be asked if a similar intervention will be useful to community-based HF patients and which aspects of COMPASS they feel is relevant and important in HF. Issues around potential barriers and facilitators for implementation will also be explored.

Procedure for the Qualitative telephone/online interviews

For the community-based HF patients, qualitative telephone/online interviews will be conducted with each participant at their preferred time and method. Due to COVID-19, the participants will be interviewed in their own home at a time that suits them. Qualitative telephone/online interviews may take 60-90 minutes. The consent form will be sent online to community-based HF patients who have access to the internet and email. Participants who do

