not have internet access a recorded consent over the telephone will be obtained. This will be done by the researcher who will read the consent form to the participants and they will be asked for their verbal consent on each statement and their answer will be recorded e.g. Do you agree to...? YES, NO. Once consent is obtained, the researcher will email the community-based HF patients a video link to COMPASS before they engage with qualitative telephone/online interviews. This video link is a demonstration of the COMPASS web-based intervention and the researcher will encourage them to view the video so they can share their views about COMPASS during the qualitative telephone/online interview. For participants who do not have access to email or the internet, the COMPASS will be explained to them by the researcher. They will be encouraged to explore the concept of web-based intervention, what services and resources the clinicians need to consider when introducing web-based interventions to people who do not have access to the internet etc.

At the start of the qualitative telephone/online interviews, rapport will be established with the participant in person (Burke & Miller, 2001; Carr & Worth, 2001) and predeveloped interview script will be used to introduce the study at the beginning of the interview (Burke & Miller, 2001). The discussion with community-based HF patients will include their perspectives about depression and anxiety assessment and management process and what they think of web-based intervention. Then, the participants will be asked about using web-based intervention for the management of depression and anxiety in general and about COMPASS intervention in specific if they have viewed the video. The participants will be asked if they think that a web-based intervention will be applicable to them and if they feel that it can be useful in HF. Also, the community-based HF patients will be asked to identify the potential barriers and facilitators for implementation of any web-based intervention.

Data to be collected

The demographic form will be sent to community HF nurses and they will be asked to complete and return this via email to the researcher before the online focus group.

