The demographic form will also be emailed to community-based HF patients and they will also be asked to complete and return this via email to the researcher before the qualitative telephone/online interview. For community-based HF patients who do not have email access, the researcher will read the information required from the baseline demographic form and will ask them to provide an answer before the interview starts.

Data handling and record keeping

Data collection will include note taking, digital encrypted Dictaphone and remarking participants' nonverbal cues when possible. The online focus groups using encrypted Microsoft (MS) teams with community HF nurses will be audio recorded using digital encrypted Dictaphone. The qualitative telephone/online interviews with community-based HF patients will be in a private room and will be audio-recorded using digital encrypted Dictaphone. The participants will be assured that privacy and confidentiality will be maintained, as the researcher will be sitting alone in a private room during the interview.

Field notes on the group interactions and processes will also be transcribed by the researcher. Thematic analysis assisted by N-vivo 12 will be used to allow the development and 'saturation' of themes and categories.

An online consent form will be sent to community HF nurses which will be signed prior to the scheduled online focus group. For community-based HF patients, the consent form will be recorded at the start of the interview, and the participant will be asked whether they agree with each statement read by the researcher e.g. Do you agree to...? YES, NO.

All the online collected consent forms, participants personal data and qualitative data recordings and transcripts will be encrypted before they are uploaded to a secure and encrypted cloud storage area provided by KCL and will only be accessible by researcher and the two co-investigators. Once the study has been completed, the recordings will be destroyed by deleting them from the encrypted and password protected file sharing cloud.

Sample size:

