During recruitment of the participants, the researcher will discuss the purpose of the study and the criteria for participation. The researcher will assure all the participants that anonymity will be provided, and they can withdraw at any time. Participants will also be informed that no harm will result from taking part in the study or even by refusing to participate. It is not anticipated that participation in the study will be stressful. However, before the online focus group or qualitative telephone/online interviews commences, it will be explained to all participants that they do not have to answer any questions they do not wish to or that make them uncomfortable. In addition, the online focus group will be co-facilitated by the co-investigator who is a mental health lecturer with extensive experience in clinical mental health practice and psychological therapy.

Moreover, it will be clearly explained to all participants that all data will be pseudo-anonymised during transcription and that data will be stored securely under a study number whereas

comments quoted in any reports, results, published papers or feedback will not be linked to any individual.

Reporting and dissemination

The study will be published in a peer-reviewed scientific journal.

References

ACCF &AHA. (2013). 2013 ACCF/AHA Guideline for the Management of Heart Failure. *Journal of American College of Cardiology*, 62 (16, 147-239).

American Heart Association (2017). Classes of heart failure. Retrieved from <https://www.heart.org/en/health-topics/heart-failure/what-is-heart-failure/classes-of-heart-failure> on 29 Dec 2018

American Heart Association (2017). What is Heart Failure? Retrieved from <https://www.heart.org/en/health-topics/heart-failure/what-is-heart-failure> on 24 NOV 2018

American Psychiatric Association (2017). Depression. retrieved from <https://www.psychiatry.org/patients-families/depression/what-is-depression> on 24 NOV 2018

Barbour, R., S. (2005). Making sense of focus groups. *Medical Education*, 39 (7), 742-750. <https://doi.org/10.1111/j.1365-2929.2005.02200.x>

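### The protocol has participants told that taking part will cause no harm, a guarantee it cannot give to patients selected for current depressive symptoms

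*Protocol*

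**What the plan says.** Ethical considerations describes what the researcher says during recruitment. After promising anonymity and the right to withdraw, it states: "Participants will also be informed that no harm will result from taking part in the study or even by refusing to participate". The next sentence is weaker: "It is not anticipated that participation in the study will be stressful". The one after that has participants told, before the session begins, that "they do not have to answer any questions they do not wish to or that make them uncomfortable".

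The patients who receive this assurance are defined under Subject inclusion criteria as those "who have mild to moderate symptoms of depression with/without anxiety confirmed by PHQ-9 (5-14) and GAD-7". The Procedure for the Qualitative telephone/online interviews gives the length ("Qualitative telephone/online interviews may take 60-90 minutes") and the content: "The discussion with community-based HF patients will include their perspectives about depression and anxiety assessment and management process". The sample is five nurses and eight patients.

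**The concern.** A statement about risk, made while someone is deciding whether to take part, has to be one that the study can stand behind. This one is absolute. The patients who hear it are selected for current low mood and are then asked to talk at length about depression and anxiety. Some distress is foreseeable in that setting, even if it is uncommon and short-lived, so the promise may turn out to be untrue for a particular patient. At stake is honest disclosure to a vulnerable group. No theme, code or conclusion of the study depends on it.

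**Working it through.** No calculation applies. The study is qualitative, the protocol gives no rate of distress, and the question is whether the document supports the assurance. The check sets the relevant texts side by side.

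1. **Scope of the assurance.** It is addressed to participants in general: 5 nurses + 8 patients = 13, which agrees with the Sample size section. It names two situations, taking part and refusing, and contains no qualifier such as *expected* or *serious*.

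2. **Its own paragraph.** Three consecutive statements differ in strength:
   - a fact about the future: there will be no harm;
   - an expectation: stress is not anticipated;
   - a concession, introduced by *However*: some questions may cause discomfort and can be skipped.

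   The second and third are reasonable. They support *no harm is expected*, which is weaker than *no harm will occur*. The first sentence therefore claims more than the two that follow it.

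3. **Who is interviewed.** Entry requires a PHQ-9 score of 5-14, so current depressive symptoms are a condition of selection. The exclusion criteria remove severe depression and suicidal ideation. That lowers the risk but does not bring it to zero.

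4. **What they are asked.** The interview topics include depression and anxiety assessment and management, over 60-90 minutes. Study objectives and purpose adds a further sensitive aim: "This study will explore the impact of COVID-19 on the psychological wellbeing of community-based HF patients". The interview procedure does not list the pandemic among its topics, so the point does not rely on it.

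5. **Any withdrawal of the statement elsewhere.** There is none in the protocol. The rights to skip questions and to withdraw are protections. They do not qualify the promise.

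Result: the assurance is stronger than anything else in the document supports, and the group for whom it matters most is the one selected for symptoms.

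**The case against.** The best defence is that the sentence is a loosely drafted no-penalty clause. Harm from refusing can only mean being disadvantaged, and the sentence follows directly on the right to withdraw. That reading suits the second half. It does not suit the first half, which expressly speaks of taking part, and if no penalty was all that was meant, the protocol should say so.

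A second defence is that the paragraph as a whole tells patients, before any question is put, that they may find some questions uncomfortable. This stands as mitigation and is a reason to call the fault minor. It does not make the earlier sentence correct.

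A third is that the information sheet and consent form are what patients actually read, and neither is shown. This also stands. It means that the criticism is of the protocol's instruction, and nothing can be concluded about the consent that patients would in fact give.

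Three stronger readings are tempting, and the documents do not support them:

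- **That patients have no support if they become distressed.** A reader might infer this because "the researcher will be sitting alone in a private room during the interview" and because the co-investigator with mental-health experience is mentioned only for the nurses' focus group. The quoted words are a privacy assurance, given to explain why confidentiality is kept. They do not show that supervision or back-up is absent.
- **That the lack of a distress or referral procedure is itself an error.** It is detail that this document does not give and may sit elsewhere. It is not something the protocol states wrongly.
- **That the chance of harm can be put as a number.** Any figure would rest on an invented per-interview rate, and distress is not the same thing as harm. The point needs no figure, because an absolute promise is unsupported at any risk above zero.

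**Conclusion.** The sentence is wrong as written. The protocol instructs that an unqualified promise of no harm be given at recruitment, while its own next sentences support only an expectation. The promise matters for all eight patients, because each is selected for current depressive symptoms and interviewed about depression and anxiety.

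This is a minor correction of consent wording. The sampling, the data and the thematic analysis are unaffected. The conclusion rests on reading the sentence in its ordinary sense, and on there being some risk of distress, however small, in an interview of this kind. It does not rest on any assumed rate, nor on any claim that safeguards are missing. If the information sheet is already worded more carefully, what remains is a mismatch between it and the protocol.

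**What to change.** Replace the sentence in Ethical considerations with wording such as: *No serious harm is expected, but talking about depression or anxiety may cause some distress; you may skip questions, pause or stop at any time, and declining or withdrawing will not disadvantage you or affect your care.* Keep the existing text on skipping questions and withdrawing, and align the information sheet with the new wording.

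The cost is one sentence, with no added staff, contacts or data. A few patients may be slightly more hesitant to take part, which is an acceptable price for an accurate statement. The same section says that the application for NHS approval is still being prepared, so on the document's own timeline the change can be made before submission.

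The correction does not need a prescribed notification procedure. In particular, reporting disclosures to the patient's heart failure nurse for IAPT or 3DLC referral should not be written in on the strength of this point. The Introduction describes those services as routine treatment chosen by severity, not as an urgent-risk route. The community nurses also identify the patients and are themselves participants, so such a rule could make patients less open about how their depression and anxiety are managed.
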